9.4 DATA SOURCES

No additional diagnostic or monitoring procedures will be applied to the patients because of a retrospective study, and this study plans to collect the data onto the designed CRF as only those are available in the medical records. The data source includes medical records in ~ 12 hospitals in Taiwan, where pulmonologists licensed with specialty care for respiratory diseases (COPD included) and critical care medicine.

Each patient is identified by a unique subject/initial number, which is only used for study purposes.

9.5 STUDY SIZE

Based on the projected market share and per physician's clinical experience, data from approximately 1,800 patients will be collected.

Among these patients, using Tio + Olo FDC versus other LABA/LAMA therapy (FDC or free combo) is assumed the ratio of 1:2 (~ 300 Tio + Olo, ~ 800 other LABA/LAMA therapy). If we assume the same annualized event rates as in the Taiwanese subgroup analysis report of DYNAGITO¹ (i.e. 0.78 per patient-year for Tio + Olo and 0.90 per patient-year for other

therapies), expecting the 95% CI for incidence rate ratio to be 0.87 (0.768, 0.978), with good precision. The following **Table 2** also shows that with smaller sample size, the precision is reduced (wider 95% CI).

Table 2 Sample size estimation

| Tio + Olo | | Other | | Incidence rate ratio (95% CI) |
|---------------------|-------------|---------------------|-------------|-------------------------------|
| True Incidence rate | Sample size | True Incidence rate | Sample size | |
| 0.78 | 300 | 0.90 | 800 | 0.87 (0.768, 0.978) |
| 0.78 | 300 | 0.90 | 300 | 0.87 (0.751, 1.000) |
| 0.90 | 300 | 0.97 | 800 | 0.93 (0.829, 1.039) |
| 0.90 | 300 | 0.97 | 300 | 0.93 (0.810, 1.062) |
| 0.90 | 200 | 0.97 | 200 | 0.93 (0.786, 1.094) |
| 0.90 | 200 | 0.97 | 100 | 0.93 (0.734, 1.173) |

In this table, it is assumed that all patients have on average ~ 2 patient-year exposure.

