9.3.2 Outcomes

9.3.2.1 Primary outcomes

- Time to the first moderate or severe COPD exacerbation

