9.7.1 Main analysis

The propensity score matching approach* will be used to balance the baseline characteristics between the study cohorts. These data will be compared descriptively between patients receiving different regimens (Tio + Olo vs. other LABA/LAMA vs. LAMA). If the propensity score matching is done, the difference before and after matching will be considered both.

For the primary outcome

Time to the first moderate or severe COPD exacerbation will be compared between different cohorts using Kaplan-Meier curves with the incidence and time to events, and statistical significance will be assessed using log-rank tests.

Time to first acute exacerbation starts from the index date to the date of the first acute exacerbation recorded on the CRF. Patients with exacerbation free at the time of escalating to ICS or no documented with exacerbations will be censored.

For secondary outcomes

- Time to escalating to dual/triple therapy will also be analysed using Kaplan-Meier curves and log-rank tests.
- The annualized rate of exacerbation with various severity will be calculated for each study group (episodes/patient-year), and the differences between the three cohorts will be compared by rate ratio.
- Results of lung function (i.e., spirometry data) and COPD assessments (i.e., CAT and mMRC) will be evaluated by the change from baseline. Pair *t*-test or other applicable statistical methods will be used for assessing the intra-group difference under a significance level of 0.05.
- Chi-square test or Fisher's exact test will be applied for categorical variables such as reasons for switching/escalating therapies, frequency, and percentage, etc.

*NOTE: Variables may include but not limited to age, gender, disease duration before index date, smoking status, body mass index, COPD assessment score (e.g., CAT and mMRC), spirometry data (e.g., FEV₁), oxygen therapy, comorbidities, disease severity, previous exacerbation, previous treatments, or eosinophil counts, where appropriate.

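### Section 9.5 claims good precision from a secondary rate ratio at an exposure the design cannot reach, and gives none for the primary time-to-first-event comparison

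*Combined protocol and SAP*

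**What the plan says.** The single primary outcome in Section 9.3.2.1 is "Time to the first moderate or severe COPD exacerbation". Section 9.7.1 compares it by Kaplan-Meier curves and log-rank tests. The annualized exacerbation rate, compared by rate ratio, is a secondary outcome (Sections 9.3.2.2 and 9.7.1).

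Section 9.5 takes the total of about 1,800 patients from market share and clinical experience. For cohorts A and B it "is assumed the ratio of 1:2 (~ 300 Tio + Olo, ~ 800 other LABA/LAMA therapy"), with rates of "0.78 per patient-year for Tio + Olo and 0.90 per patient-year for other" therapies, and concludes by "expecting the 95% CI for incidence rate ratio to be 0.87 (0.768, 0.978), with good precision". Table 2 has six rows, all of them rate ratios. They include equal cohorts of 300 at the same rates, "0.78 | 300 | 0.90 | 300 | 0.87 (0.751, 1.000"), and smaller sets at other rates, such as "0.90 | 200 | 0.97 | 200 | 0.93 (0.786, 1.094"). The note under the table says that "it is assumed that all patients have on average ~ 2 patient-year exposure".

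The abstract and Section 9.1 end follow-up at death or 1 year after the index date, whichever comes first. Section 9.7.1 says that propensity score matching "will be used to balance the baseline characteristics between the study cohorts", and then that, if it is done, results before and after matching are both considered. Section 9.7 names all eligible patients as the main analysis population. Section 9.5 does not mention matching.

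**The concern.** The one quantitative argument for the study size describes a different quantity from the primary comparison. A rate ratio counts every exacerbation, whereas time to first event uses at most one per patient. The table also credits each patient with more follow-up than the design allows, and it makes no allowance for patients left out by matching. All three make the printed interval narrower than the primary comparison can deliver.

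What is at stake is how the result is read. If the assumed effect were real, the primary log-rank test would more likely than not be non-significant. A reader who relied on Section 9.5 could then take that as evidence of no difference.

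**Working it through.** **Inputs.** Rates 0.78 and 0.90 per patient-year, cohorts of 300 and 800, and about 2 patient-years each (Section 9.5); follow-up of at most 1 year (abstract, Section 9.1). The ratio is 0.78/0.90 = 0.867, with log −0.143.

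**Step 1: reproduce the stated interval.** For a rate ratio with Poisson counts, SE(log ratio) = √(1/(r₁n₁t) + 1/(r₂n₂t)), and the limits are ratio × exp(±1.96 SE). For 300 vs 800:

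| Years per patient | Events | SE | 95% CI |
|---|---|---|---|
| 2 (as stated) | 468 + 1,440 | 0.053 | 0.781, 0.962 |
| 1.5 | 351 + 1,080 | 0.061 | 0.768, 0.978 |
| 1 (design maximum) | 234 + 720 | 0.075 | 0.748, 1.004 |

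The printed interval does not come from 2 patient-years; it matches 1.5. Rows 1 to 5 of Table 2 all match 1.5 to within 0.001. Row 6, labelled 200 vs 100, does not: at 1.5 years those sizes give (0.758, 1.135), while 100 vs 100 gives the printed (0.734, 1.173). Overdispersion at 2 years does not explain the table either, because the negative binomial dispersion needed varies from 0.18 to 0.43 across rows. At the 1-year cap, the headline rate ratio already includes 1.

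**Step 2: first-event precision at 1 year.** Assume constant hazards, full 1-year follow-up, that the two rates are moderate-or-severe rates, and that the hazard ratio equals the rate ratio. Expected first events are n(1 − exp(−r)): 54.2% of Tio + Olo patients and 59.3% of the others. SE(log HR) = √(1/d₁ + 1/d₂). The stated log width is ln(0.978/0.768) = 0.242.

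| Set | First events | SE | 95% CI around 0.87 | Log width | Ratio to stated |
|---|---|---|---|---|---|
| 300 vs 800, unmatched | 162 + 475 | 0.091 | 0.725, 1.036 | 0.356 | 1.47 |
| 300 vs 600, matched 1:2, no loss | 162 + 356 | 0.095 | 0.720, 1.043 | 0.371 | 1.54 |
| 300 vs 300, matched 1:1, no loss | 162 + 178 | 0.109 | 0.701, 1.072 | 0.425 | 1.76 |

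Power for the unmatched set is Φ(0.143/0.0909 − 1.96) = Φ(−0.39), about 35%. At 1:1 it is Φ(0.143/0.1085 − 1.96) = Φ(−0.64), about 26%. If only 200 pairs could be formed (an assumption), the interval would be (0.668, 1.125).

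**Step 3: separate the causes.** For 300 vs 800, moving the rate ratio from the fitted 1.5 years to 1 year widens the log interval by a factor of 1.22. Counting first events only adds a further 1.47/1.22 = 1.21. The two contribute about equally. Matching then adds 1.54/1.47 = 1.05 at 1:2, or 1.76/1.47 = 1.19 at 1:1.

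**Step 4: keep the stated 2 years.** First events become 237 + 668, SE is 0.076 and the interval is (0.747, 1.005). The endpoint mismatch is therefore enough, without the exposure correction, to bring 1 into the interval.

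**The case against.** Several stronger readings are tempting and should be resisted.

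- **That 300 vs 800 is the only precision shown.** It is not. Table 2 gives equal cohorts of 300, reaching 1.000, and Section 9.5 says smaller samples lose precision. Part of the cost of smaller cohorts is thus visible, though only for the rate ratio and not presented as a matched set.
- **That the main analysis is clearly the matched one.** Section 9.7 names all eligible patients, and Section 9.7.1 both plans matching and makes it conditional. The text is unclear, so both sets need figures.
- **That the interval is 1.8 times too narrow because of matching.** This needs a 1:1 ratio, which the visible text does not state. At 1:2 with no loss, matching changes little. Much of the widening comes from exposure. Set against the table's own 300 vs 300 row (log width 0.286), first events in the same patients at the fitted 1.5 years give (0.717, 1.047), width 0.379, which is about 1.3 times.
- **That the plan promises a primary result excluding 1.** It does not. Section 9.5 labels the interval as an incidence rate ratio, states no power target, and the primary objective is to understand how often exacerbations occur. The power figures describe what the log-rank test could do; they do not show that a stated target was missed.

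In addition, the visible primary analysis names no hazard ratio, and the subsection between 9.7.1 and 9.7.3 is redacted. A model or matching detail there cannot be ruled out.

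None of this supplies precision for the primary outcome in Section 9.5, or reconciles 2 patient-years with a 1-year cap.

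**Conclusion.** The point holds in this limited form. Section 9.5 claims good precision from a secondary measure, at an exposure that disagrees both with its own table and with the design, and it says nothing about the primary comparison or the effect of matching. With follow-up at the design maximum, the headline rate ratio no longer excludes 1. For the primary comparison the interval is about 1.5 times the stated log width in all eligible A and B patients, and up to about 1.8 times if matching is 1:1 without loss. It includes 1 in every case examined.

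The first-event figures rest on the assumptions in Step 2; the rate-ratio correction does not need them. Full follow-up is the favourable case. An assumed censoring hazard of 0.2 per year gives (0.720, 1.044) unmatched, and strong between-patient variation (gamma frailty variance 1) gives (0.711, 1.057). Since imputation is barred and candidate score variables may be missing from charts, the no-loss matched figures are also best cases.

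**What to change.** In Section 9.5:

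1. Recompute every row of Table 2 at no more than 1 patient-year, correct the exposure note, check the cohort sizes in the last row, and label the table as the secondary rate ratio before matching.
2. Add a short table for the primary outcome at 1 year: expected first events and the interval for the ratio, for all eligible patients and for the planned matching ratio, with an allowance for unmatched patients. State that ratio in Section 9.7.1, and say which set is primary.
3. State whether 0.78 and 0.90 are moderate-or-severe rates.
4. Remove the claim of good precision.

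The cost is some rewording and one added table. No extra patients or data are needed. The stated figures become less favourable.

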| Study design: | 
This is a retrospective, multi-center, cohort study to collect the data on COPD patients who were administered with LABA/LAMA (FDC or free combo) or LAMA treatment for 3 months at least prior to 30 June 2018. For LABA/LAMA therapy, new initiation or switching from other therapy (i.e., single/dual/triple) are both acceptable; for LAMA
 | | |

Proprietary confidential information © 2019 Boehringer Ingelheim International GmbH or one or more of its affiliated companies

| | |
|--------------------|---|
| | 
treatment, only new initiation will be acceptable. The data abstracted from eligible patients will be recorded only when they are available in the medical chart and will be categorized into the cohort A (patients treated with Tio + Olo), B (patients treated with other LABA/LAMA therapy), and C (LAMA therapy).
 
The follow-up period for each patient will be from the index date* until the date of death or 1 year after the index date, whichever occurs first. Patients will be censored at the time from one LAMA/LABA or LAMA switched to another LAMA/LABA or ICS.
 
*Index date: It is defined as the date of COPD patients in the cohort A and B starting using LABA/LAMA therapy regardless of new initiation or switching from other single/dual/triple treatment, or the date of the patients in the cohort C starting using LAMA treatment.
 |
| Population: | 
This study plans to review the medical chart from approximately 1,800 COPD patients receiving LABA/LAMA or LAMA treatment for 3 months at least prior to June 30 2018 in Taiwan.
 
Inclusion criteria
 
Patients who fulfil ALL the following criteria are included.
 
1. Patients who diagnosed with COPD who were prescribed with LABA/LAMA (FDC or free combo) as a new initiation or switching from other therapy (i.e., single/dual/triple), or newly receiving LAMA treatment for 3 months at least prior to 30 June 20182. Male or female patients ≥ 40 years of age 
Exclusion criteria
 
Patients who meet the following criterion are not included.
 
1. Patients with documented diagnosis of bronchial asthma, asthma-COPD overlap syndrome (ACOS), bronchiectasis, cystic fibrosis, or lung cancer |

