| Variables: | 
Variables
 
• Patient demographics (date of birth, gender, race, body mass index [BMI], family history, occupation, etc.)• Diagnosis of COPD (date of diagnosis, disease severity, etc.)• Smoking status• Spirometry data (e.g., FEV₁, FVC)• COPD assessments (e.g., CAT, mMRC)• Acute exacerbations from 1 year before the index date until 1 year after the index date or the date of death (onset/stop date, etc.)• Hospitalizations due to COPD exacerbation (e.g., admission/discharge date, treatments)• Laboratory data (e.g., eosinophil counts) |

Proprietary confidential information © 2019 Boehringer Ingelheim International GmbH or one or more of its affiliated companies

| | |
|-----------------------|--|
| | 
• Pharmacological/non-pharmacological treatments from 6 months before the index date to 1 year after the index date or the date of death, especially for the following:
- Treatment related to COPD (start/stop dates, dosage, frequency, etc.)- Rescue treatments for COPD (antibiotics, oral corticosteroid, ventilator support, etc.)- Oxygen therapies- Surgeries for COPD therapy or improvement of lung function• Time/reasons for treatment switching (e.g., single/dual/triple therapy to LABA/LAMA prior to the index date, Tio + Olo to other therapies, single/dual escalating to dual/triple therapy)• Comorbidities (cardiovascular, cerebrovascular, respiratory, hepatic, renal, gastrointestinal, metabolic, infectious comorbidities, etc.) |
| | 
Primary outcomes
 
• Time to the first moderate or severe COPD exacerbation |
| | 
Secondary outcomes
 
• Annualized rate of mild/moderate/severe exacerbation• Time/reason (e.g., severe airflow limitation, diagnosis of asthma, worsening exacerbation) from LABA/LAMA escalating to LABA/LAMA/ICS or from LAMA to dual therapy• Percentage of patients receiving LABA/LAMA switched to triple therapy or LAMA switched to dual therapy• Change in pulmonary function after LABA/LAMA or LAMA initiation• Use of rescue medications |
| Data sources: | Source data are collected from medical charts in 12 medical hospitals in Taiwan. The case report form (CRF) will be designed for the data collection. |
| Study size: | Approximately 1,800 eligible COPD patients are planned to be enrolled from 12 medical hospitals in Taiwan. |

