9. RESEARCH METHODS

9.1 STUDY DESIGN

It is a retrospective, multi-center, cohort study to collect the data on COPD patients who were administered with LABA/LAMA (FDC or free combo) or LAMA therapy for 3 months at least prior to 30 June 2018. The patients using LABA/LAMA therapy will be enrolled regardless of new initiation or switched from other single/dual/triple treatment, whereas those using LAMA treatment will only be acceptable when LAMA is newly initiated. This study aims to estimate the occurrence of COPD exacerbation in the COPD population under the real-world practice in Taiwan. Additionally, the study also assesses outcomes of clinical characteristics and prescription patterns for patients using LABA/LAMA or LAMA. After Institutional Review Board's (IRB) permission, it will be carried out in around 12 medical centers in Taiwan and plans to collect the clinical data abstracted from the medical charts of approximately 1,800 eligible patients. The eligible patients will be separated into three cohorts based on the prescription for COPD on the index date. Cohort A includes the patients treated with Tio + Olo, cohort B is the patients treated with other LABA/LAMA therapy, and cohort C is the patients receiving LAMA treatment. No investigational or interventional treatment will be provided in the retrospective study.

The retrospective study will review medical charts of COPD patients with LABA/LAMA or LAMA therapy until death or 1 year after the index date, whichever occurs first. The data collection will be conducted after eligibility assessment. Medical records will be reviewed and relevant information will be abstracted for various details such as patient demographics, diagnosis of COPD, smoking status, records of exacerbations and hospitalization, examinations of lung function and laboratory, treatments related to COPD or comorbidities, reasons for treatment switching, and comorbidities.

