9.2.3 Study visits

The abstracted data will be recorded on the case report form (CRF). **Table 1** shows the collected data at different retrospective period of the medical chart.

Table 1 Data collection schedule

| Variables | Time points | Eligibility assessment | Data collection retrospectively | | |
|----------------------------------|-------------|------------------------|---------------------------------|-------------------------|--------------------------------------|
| | | | Before the index date | Index date [#] | 1-year follow-up period [†] |
| Eligibility assessments | X | | | | |
| Demographics ¹ | | | | X* | |
| Diagnosis of COPD ² | | | | X* | |
| Smoking status ³ | | | | X* | |
| Comorbidity ^{4, §} | | X [◊] | X | X | |
| COPD assessments [‡] | | | | | |
| CAT ⁵ | | X ^Δ | X | X | |
| mMRC ⁶ | | X ^Δ | X | X | |
| Examinations [‡] | | | | | |
| Spirometry data ⁷ | | X ^Δ | X | X | |
| Eosinophils | | X ^Δ | X | X | |
| Records [‡] | | | | | |
| Acute exacerbations ⁸ | | X ^{&} | X | X | |
| Hospital admissions ⁹ | | X ^{&} | X | X | |
| Treatments | | | | | |

| Variables | Time points | Eligibility assessment | Data collection retrospectively | | |
|--|-------------|------------------------|---------------------------------|-------------------------|--------------------------------------|
| | | | Before the index date | Index date [#] | 1-year follow-up period [†] |
| Related to COPD ^{10, \$} | | | X ^{11, ♦} | X | X |
| Related to comorbidities ^{12, \$} | | | X [◊] | X | X |
| Rescue treatments ^{13, ‡} | | | X [◊] | X | X |
| Oxygen therapy ^{14, \$} | | | X [◊] | X | X |
| Others ^{15, \$} | | | X [◊] | X | X |

[#]Not later than 30 June 2018; defined as the date of COPD patients in the cohort A and B starting using LABA/LAMA therapy regardless of new initiation or switching from other single/dual/triple treatment, or the date of the patients in the cohort C starting using LAMA treatment

[†]Not later than 1 year after the index date

^{*}The data nearest to the index date will be collected.

[◊]The data 6 months before the index date will be documented.

^{\$}The data will be collected every 6 months (allowed window: ± 1 month).

[‡]All available data on the medical chart will be recorded.

[△]The data nearest to the index date will be collected as the **Baseline**.

[&]The data/events ever since patients started receiving LABA/LAMA or LAMA therapy will be collected (maximum: trace back to 1 year before the index date).

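### Section 9.5 bases its precision on about 2 patient-years per patient although follow-up stops at 1 year, and Table 2 is also inconsistent with itself

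*Combined protocol and SAP*

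**What the plan says.** Section 9.5 takes the planned 1,800 patients from expected market share and physicians' experience, then describes the precision this would give for Tio + Olo against other LABA/LAMA therapy. It assumes about 300 and 800 patients, calls that split 1:2, and uses annualized rates of 0.78 and 0.90. It reports "expecting the 95% CI for incidence rate ratio to be 0.87 (0.768, 0.978), with good precision". Table 2 gives six scenarios, and its footnote states: "In this table, it is assumed that all patients have on average ~ 2 patient-year exposure".

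The follow-up rules appear elsewhere:

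- Abstract, Study design: follow-up runs from the index date "until the date of death or 1 year after the index date, whichever occurs first".
- Abstract, Study design: "Patients will be censored at the time from one LAMA/LABA or LAMA switched to another LAMA/LABA or ICS".
- Section 9.1: charts are reviewed "until death or 1 year after the index date, whichever occurs first".
- Section 9.2.3, Table 1 footnote to the follow-up column: "Not later than 1 year after the index date".

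The Abstract (Variables) also lists "Acute exacerbations from 1 year before the index date until 1 year after the index date or the date of death", which is a two-year window for recording events.

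**The concern.** If no patient can contribute more than 1 year after the index date, average exposure cannot be about 2 patient-years. The number of events drives the width of a rate-ratio interval, so overstating exposure overstates precision. Table 2 is the only quantitative support for the study size, and a reader will take from it that the interval for the assumed effect lies wholly below 1. If that depends on exposure the design cannot supply, the statement is wrong as written. Two further signs suggest the table was not checked: the last row's limits look too wide for its sample sizes, and the stated ratio does not match the stated counts.

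**Working it through.** **Inputs.** Rates, sample sizes and printed limits come from Table 2; the 1-year cap comes from the Abstract, Section 9.1 and Table 1. The protocol gives no CI method, so I assume the usual one: Poisson events and a two-sided 95% Wald interval on the log rate ratio,

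CI = (r1/r2) × exp(±1.96 × √[1/(r1·n1·T) + 1/(r2·n2·T)]),

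with T the mean patient-years per patient.

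**Does the two-year recording window supply 2 patient-years?** No. The index date is the start of the treatment that defines the cohort, so the preceding year is not exposure to that treatment. The rates 0.78 and 0.90 are treatment-specific, and Section 9.7.1 lists previous exacerbation as a candidate propensity-score variable, that is, as baseline history.

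**Row 1 worked through.** r1/r2 = 0.78/0.90 = 0.8667. At T = 1 the expected events are 0.78 × 300 = 234 and 0.90 × 800 = 720. Then √(1/234 + 1/720) = 0.07525, 1.96 × 0.07525 = 0.1475, and the CI is 0.748 to 1.004. At T = 2 (468 and 1,440 events) it is 0.781 to 0.962. At T = 1.5 it is 0.768 to 0.978, the printed interval.

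**All rows.** The last column is the exposure that reproduces the printed width.

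| Row | n (Tio + Olo / other) | Printed | T = 2 | T = 1.5 | T = 1 | Implied T |
|---|---|---|---|---|---|---|
| 1 | 300 / 800 | 0.768–0.978 | 0.781–0.962 | 0.768–0.978 | 0.748–1.004 | 1.489 |
| 2 | 300 / 300 | 0.751–1.000 | 0.766–0.981 | 0.751–1.000 | 0.727–1.032 | 1.495 |
| 3 | 300 / 800 | 0.829–1.039 | 0.841–1.023 | 0.829–1.039 | 0.808–1.066 | 1.505 |
| 4 | 300 / 300 | 0.810–1.062 | 0.825–1.043 | 0.810–1.062 | 0.786–1.095 | 1.495 |
| 5 | 200 / 200 | 0.786–1.094 | 0.804–1.071 | 0.786–1.095 | 0.757–1.136 | 1.505 |
| 6 as labelled | 200 / 100 | 0.734–1.173 | 0.779–1.105 | 0.758–1.135 | 0.725–1.188 | 1.109 |
| 6 if 100 / 100 | 100 / 100 | 0.734–1.173 | 0.757–1.136 | 0.734–1.173 | 0.696–1.236 | 1.50 |

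Rows 1 to 5 agree with 1.5 patient-years to rounding. Row 6 agrees only if both groups have 100 patients. No single exposure fits all six rows as labelled.

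**Other interval methods.** Exact conditional and linear-scale Wald intervals reproduce no row at T = 2 or T = 1; for row 1 they give 0.779–0.963 and 0.776–0.957 at T = 2, and 0.745–1.006 and 0.739–0.994 at T = 1. A 90% interval for row 1 at T = 1 is 0.766–0.981, close to the printed one but not equal to it.

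**Size of the effect, row 1.** The printed log width is ln(0.978/0.768) = 0.242. At T = 1 it is 2 × 0.1475 = 0.295, and 0.295/0.242 = 1.22, so 22% wider. The upper limit falls below 1 only if T exceeds about 1.06: ln(1/0.8667) = 0.1431, (0.1431/1.96)² = 0.00533, and 0.00566/0.00533 = 1.06.

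**Sensitivity, row 1 (assumptions not in the protocol).**

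- Mean exposure 0.8 patient-years after censoring: 0.735 to 1.022, 36% wider on the log scale than printed.
- Negative-binomial dispersion of 0.2 to 0.5 at T = 1: 0.739–1.016 to 0.728–1.032.

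**Ratio.** 800/300 = 2.67, so the counts are 3:8. A 1:2 split with 300 would be 300:600, which at T = 1 gives 0.743 to 1.010.

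**The case against.** The strongest counter-argument concerns method. Because the protocol does not name one, the printed limits could come from 2 patient-years with an unstated overdispersion allowance. A constant variance factor of 4/3 at T = 2 is algebraically the same as Poisson at T = 1.5, so it reproduces rows 1 to 5 equally well. This stands: the documents cannot separate the two readings, and the recomputed limits are conditional on the Poisson form. It does not rescue the table, though. Two years would still breach the follow-up cap, and the same factor at 1 patient-year gives row 1 as 0.731 to 1.028, wider than the Poisson result. Nor does it explain row 6, since a constant factor acts like one common exposure. A negative-binomial dispersion of 0.2 at 2 years comes within 0.004 of rows 1 to 5 but gives 0.756 to 1.139 for 200 versus 100, so it does not explain row 6 either.

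A second point is proportion. Table 2 does not determine the 1,800 and concerns the rate ratio, a secondary outcome; the primary time-to-first-event outcome is not sized at all. Section 9.5 sets no power, margin or target width, so an upper limit of 1.004 rather than 0.978 crosses no stated threshold. That is fair and limits the consequence to the precision statement. The statement remains incorrect.

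Third, the footnote's approximate 2 may be 1.5 rounded up, in which case the mismatch in rows 1 to 5 is the same defect and not a second one. That is plausible, but 1.5 also exceeds the cap. The approximation signs on 300 and 800 make the ratio point editorial.

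**Conclusion.** The concern holds. The contradiction between about 2 patient-years and a maximum of 1 needs no statistical model. Under a Poisson log-rate-ratio interval, the headline CI at the maximum permitted exposure is 0.748 to 1.004 instead of 0.768 to 0.978: 22% wider on the log scale, and it just includes 1. Censoring at switching, overdispersion or patients lost in matching would widen it further. The printed limits in rows 1 to 5 correspond to 1.5 patient-years under that method. Row 6 is inconsistent with its label under every variance model tried; 100 versus 100 is the likely intended scenario but cannot be confirmed from the document. The 1:2 ratio disagrees with the counts used in the table. The damage is confined to what Section 9.5 promises about precision.

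**What to change.** In Section 9.5:

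- Change the exposure footnote to at most 1 patient-year and state how the intervals are calculated.
- Recompute Table 2 and the figure in the text. With the Poisson method at 1 patient-year, rows 1 to 5 become 0.748–1.004, 0.727–1.032, 0.808–1.066, 0.786–1.095 and 0.757–1.136. If the sponsor used another variance, these should be replaced by that method's values at no more than 1 patient-year.
- Correct either the label or the interval of row 6: 0.725–1.188 for 200 versus 100, or 0.696–1.236 for 100 versus 100.
- Give the ratio as 3:8, to match the counts that Table 2 uses.
- Replace the claim of good precision with a neutral description of the expected width.
- Optionally, add a row for shorter exposure, labelled as an assumption (row 1 at 0.8 patient-years: 0.735–1.022).

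The cost is a text correction and a less favourable precision statement. Enrolment, data collection, endpoints and analyses are unchanged.
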